Phenotypic Outcomes (AIM 1) and Biomarker DNA Age (AIM 2): We hypothesize that the VTEL high-intensity circuit exercise intervention will increase cardiorespiratory fitness and decrease sarcopenia and frailty (AIM 1) and decrease DNA Age (AIM 2). ANOVA models will be used with dependent variables of cardiorespiratory fitness (VO₂peak, 2-minute step test) and DNA Age (years). Logistic or multinomial models will be used with dependent variables of sarcopenia (present/not present) and frailty (robust/pre-frail/frail). Secondary analyses will be performed that use the individual components of composite outcome as their own dependent variable (e.g., lean mass and strength from sarcopenia). ANCOVA will be used to test for between group difference by time (pre/post exercise). Baseline performance and demographic and clinical characteristics will be included in models to assess and adjust for known potential confounding factors based on our experience with older HIV+ adults. We do not expect significant variability or effect from HIV-related factors (e.g., antiretroviral therapy, viral load) since we will use our previous established eligibility criteria. We do not anticipate needing to adjust for sex or race since each individual will function as their own control. Nutritional analyses of macro and micronutrients will be performed to measure any change during the study, and if present, will be tested for within group and between group effects. A similar approach will be applied to smoking exposure, which will be quantitated at baseline and follow-up testing. Treatment fidelity will be measured as percent of AEX time at target heart and entered in ANOVA models. For future planning, feasibility analyses will include calculation of rates for enrollment, retention, and attendance overall and by HIV group. Aggregate data will be collected on adverse events and reasons for lost to follow-up.

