3 STUDY METHODS

3.1 Study Design

This study is a multi-site exercise intervention for Veterans receiving care at the Atlanta and Baltimore VAMCs that will randomize approximately 80 participants (40 per site) at these VAMCs, herein referred as enrollment sites. The intervention is 12-weeks of high-intensity functional circuit exercise performed 3 times weekly in a supervised group setting. Exercise training will be led by an exercise physiologist at the Salem VAMC (coordinating site) and broadcast to the enrollment sites. HIV-infected Veterans 50 years of age and older will be enrolled at the Atlanta and Baltimore VAMCs. Eligible participants will be randomized to exercise training (N=40) or control (N=40) groups. All participants will undergo baseline testing and follow up testing after 12 weeks at their respective enrollment site. Participants in the Control Group will be instructed to maintain their baseline sedentary lifestyle (as defined in eligibility criteria) during the 12-week intervention period. After follow-up testing is complete, participants in the control group will have the option of completing 12-week exercise training (delayed entry exercise) which will be a combined home and center-based exercise program. Pre-post exercise testing will be conducted in these participants to gauge individual progress and provide individual feedback that is a benefit of study participation, but these results will not be part of the randomized trial analyses.

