AEX, aerobic exercise; RT, resistance training

progress and any issues will be discussed on the monthly VTEL conferences with Drs. [name] (Salem), [name] (Baltimore), and [name] (Atlanta).

Adherence to Exercise Training Sessions: The intervention is designed as 12-weeks of exercise training performed 3 times weekly on Monday, Wednesday, and Friday for a total of 36 sessions. However, due to federal holidays, 36 sessions may not be feasible within 12 weeks and so time allowance will be made for 36 consecutive sessions to be performed with 100% adherence. Given that occasional missed exercise sessions will occur (usually due to travel in our experience), up to 3 additional exercise sessions will be offered to allow participants to reach 36 exercise training sessions. This provision minimizes the risk of muscle strain and exercise intolerance by allowing sufficient time to reestablish training progression and is a standard approach in progressive exercise training trials.

3.2.b Randomization

After baseline testing is complete, eligible participants will be randomized 1:1 to VTEL exercise or standard of care control groups. Randomization will occur in blocks of 2-10 participants at each site. An independent statistician will provide an allocation list for each site that will be managed by an individual without access to study data or contact with participants. The size of the block may vary by site and COVID safety practices. Block randomization is routinely used in smaller trials to ensure equal distribution between groups. In this application, it also serves to adjust the cohort size of each exercise group from a minimum of one participant to a maximum of five participants.

3.2.c Delayed Entry Exercise for Control Group

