Two-minute step test (2-MST): Rationale: Cardiopulmonary exercise testing will not readily be available when the VTEL exercise program is translated to clinical care. The 2-MST correlates with VO_2 peak in older patients ($r=0.33$; $p<0.01$)⁷³ and is advocated as a surrogate measure of aerobic capacity in space limited settings⁷² Method: The test will be performed according to the Rikli and Jones protocol in which the number of times the right knee reaches a pre-determined height is counted in 2 minutes.⁷¹ The test-retest reliability is 0.88.⁷² As a secondary analysis, we will correlate the 2-MST with VO_2 peak, not previously reported in HIV+ adults.

Frailty:

Frailty phenotype: The frailty phenotype by Fried et al. will be used to measure frailty phenotype.⁷⁴

Rationale: The Fried frailty phenotype has been widely studied in HIV+ adults.⁷⁵ **Method:** The five domains of the phenotype (slowness, weakness, low activity, weight loss, and exhaustion) will be measured and scored as previously described.⁷⁴

VACS Index: Based on our research in the Veterans Aging Cohort Study (VACS)⁷⁶ and recent epigenetics literature,⁷⁷ the VACS Index will be calculated²⁷ and used as a secondary measure of frailty. The VACS Index will be calculated based on clinically available lab values, such as kidney and renal function, age, and CD4 cell count and HIV-1 RNA level (viral load).²⁷

Blood Sampling: Blood collection, storage, and testing will be performed in the Baltimore and Atlanta VAMC laboratories. The samples will be collected across multiple draws. One of the blood draws will be conducted after an overnight fast. Staff will attempt to phlebotomize the patient during the approved fasting DXA visit to minimize discomfort and inconvenience to the patient. Blood samples will be collected in appropriate tubes using established protocols per the planned assays. Plasma will be immediately separated by centrifugation at 4°C, aliquoted, then frozen at -80°C and stored until further processing and analysis. Pre/post intervention samples from the same participant will be analyzed in the same assay.

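### The frailty model named in the plan ignores the order of robust, pre-frail and frail; a pre-specified ordinal model with a rule for a sparse frail group would use the same data better

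*Combined protocol and SAP*

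**What the plan says.** Section 1.3 lists frailty as Aim 1.3, measured by the Fried phenotype and the VACS Index. Section 2.3.e states the hypothesis in one direction (exercise reduces frailty) and gives the model: "Logistic or multinomial models will be used with dependent variables of sarcopenia (present/not present) and frailty (robust/pre-frail/frail". It does not state the link function or the test statistic.

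On covariates, section 2.3.e says: "Baseline performance and demographic and clinical characteristics will be included in models". It gives no number of covariates, and it does not say whether baseline performance means the baseline frailty category in this model. It also says: "Secondary analyses will be performed that use the individual components of composite outcome as their own dependent variable".

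Section 3.3.b describes the instrument: "The five domains of the phenotype (slowness, weakness, low activity, weight loss, and exhaustion) will be measured and scored". The VACS Index is "used as a secondary measure of frailty".

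On size, section 3.1 says: "Eligible participants will be randomized to exercise training (N=40) or control (N=40) groups". Section 3.3.a expects 30% attrition, yet Table 5 there plans for 80 completers. The sample-size table in 2.3.e covers VO2peak, the 2-minute step test, chair stands and DNAm Age, but not frailty. No frailty prevalence or target effect is given.

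**The concern.** Robust, pre-frail and frail form a scale built from five scored domains. In its usual form a multinomial model treats them as three unrelated labels. It estimates two treatment coefficients (pre-frail v robust, frail v robust) and two coefficients for every covariate, from 56 to 80 people. An ordinal model puts the directional question into one coefficient.

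Two things are at stake. The first is power on a named aim, in a trial with little to spare. The second is a reportable estimate. If one arm has no frail participant at 12 weeks, the frail-versus-robust odds ratio is zero or infinite; if neither arm has one, it does not exist. A successful intervention makes this more likely. With no fallback in the plan, the remedy would be chosen after seeing the data.

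**Working it through.** **The plan's own figure.** There is none for frailty, so there is nothing to reproduce.

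**Inputs from the documents.** 40 per arm (section 3.1); with 30% attrition, 40 × 0.70 = 28 per arm (section 3.3.a). Alpha is 0.05 (section 2.3.e), taken as two-sided.

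**Assumptions not in the documents.** Control split robust/pre-frail/frail of 45/45/10, 35/50/15 or 55/40/5; a common odds ratio (OR) of 2.5 or 4 in favour of exercise; complete cases; no covariates.

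**Step 1: exercise-arm distribution.** Multiply each cumulative odds by the OR. For 45/45/10 and OR 2.5:
- Robust: 0.45/0.55 = 0.818; × 2.5 = 2.045; probability 2.045/3.045 = 0.672.
- Not frail: 0.90/0.10 = 9; × 2.5 = 22.5; probability 22.5/23.5 = 0.957, so frail = 0.0426.
- Pre-frail: 0.957 − 0.672 = 0.286 (before rounding).

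**Step 2: chance that at least one arm has nobody frail.** P = 1 − [1 − (1 − p_C)^n] × [1 − (1 − p_E)^n], where p_C and p_E are the frail shares in control and exercise.
- n = 28: 0.90^28 = 0.0523 and 0.9574^28 = 0.296, so P = 1 − 0.9477 × 0.704 = 33%.
- n = 40: 0.90^40 = 0.0148 and 0.9574^40 = 0.176, so P = 1 − 0.9852 × 0.824 = 19%.

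| Control frail share | n per arm | No effect | OR 2.5 | OR 4 |
|---|---|---|---|---|
| 5% | 28 | 42% | 66% | 77% |
| 5% | 40 | 24% | 51% | 65% |
| 10% | 28 | 10% | 33% | 49% |
| 10% | 40 | 3% | 19% | 34% |
| 15% | 28 | 2% | 16% | 31% |
| 15% | 40 | 0.3% | 7% | 18% |

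**Step 3: power.** 40,000 simulated trials per scenario. The ordinal test is the tie-corrected Wilcoxon test (the score test of the proportional-odds model, 1 df). The multinomial test is the likelihood-ratio test (2 df).

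| Control split | n per arm | OR 2.5: ordinal v multinomial | OR 4: ordinal v multinomial |
|---|---|---|---|
| 45/45/10 | 28 | 40% v 36% | 70% v 64% |
| 45/45/10 | 40 | 53% v 47% | 85% v 79% |
| 35/50/15 | 28 | 42% v 36% | 74% v 67% |
| 35/50/15 | 40 | 56% v 48% | 88% v 82% |
| 55/40/5 | 28 | 36% v 32% | 65% v 58% |
| 55/40/5 | 40 | 49% v 43% | 79% v 73% |

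Before rounding, the gain runs from 4.4 to 8.0 points.

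**Step 4: size under no effect.** Over the same splits and arm sizes, the ordinal test rejects in 4.8% to 5.1% of trials, the multinomial likelihood-ratio test in 5.7% to 6.5%, and the multinomial Pearson test in 3.8% to 5.2%.

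**Step 5: a case where proportional odds fails.** Control 35/50/15; exercise only moves frail to pre-frail (35/63/2). Ordinal power is 9% (28 per arm) and about 11% (40 per arm). The multinomial likelihood-ratio test has 42% and 56%, and the Pearson test 29% and 47%.

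**The case against.** **The text never says unordered.** True. Multinomial can also cover a cumulative-logit model, so the plan is under-specified. A reader might infer that the sponsor deliberately chose a nominal model; the documents do not show that. The generalised logit is only the usual reading. The same sentence in the SAP settles it either way.

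**The sparse cell is speculative.** In part. The frail share is assumed. The exclusions in Table 6 (severe arthritis or neurologic disease limiting ambulation, severe heart or lung disease) point to a low share. Against that, frailty itself is not excluded, only sedentary adults enter, and low activity is one of the five domains. With 40 per arm, 10% frail and no effect, an empty arm is unlikely (3%). Multiple imputation keeps 40 per arm in the analysis set, although it does not restore the lost information.

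**The gain is best-case.** This stands. Steps 1 to 3 assume exact proportional odds, and step 5 shows that the ranking can reverse sharply. The simulation also omits baseline category and site, so it compares the two tests, not the full proposed model.

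**Frailty is covered in other ways.** The VACS Index and the component analyses give supporting evidence. They do not settle how the three-level Fried category is analysed.

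**Conclusion.** The concern holds in a limited form. The plan names a multinomial model for an ordered outcome under a directional hypothesis, and it specifies neither an ordinal model nor a rule for a sparse frail category. The cost is about 4 to 8 points of power if the effect is roughly proportional across levels. There is also a material chance of an inestimable frail-versus-robust odds ratio if the frail share is about 10% or less and exercise works. Both figures rest on assumed prevalences and effects.

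Three stronger readings are tempting and should not be drawn:
- **That the analysis breaks down.** With an empty cell only the frail-versus-robust contrast fails; the overall test can still be computed.
- **That the planned test is anti-conservative.** The mild excess in step 4 belongs to the likelihood-ratio statistic. The plan names no statistic, and the Pearson test of the same table does not exceed about 5%.
- **That an ordinal model makes frailty well powered.** Among the scenarios in step 3, the ordinal test passes 80% only at OR 4 with 40 per arm, and not in all of those.

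**What to change.** In section 2.3.e:
- Make a proportional-odds model for the 12-week frailty category, with arm, baseline category and site, the main frailty analysis.
- Report the baseline-adjusted 0–5 Fried score alongside it.
- Keep the multinomial model as a sensitivity check on proportionality.
- State the fallback for an empty or sparse frail cell, and its trigger, in advance: penalised likelihood, or collapsing to robust v pre-frail/frail. Without it, the sensitivity model's frail coefficient may be infinite when it is needed.

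The cost is SAP wording, with no added participants or measurements. The downside is lost power if exercise acts on one transition only, such as frail to pre-frail. The SAP should acknowledge this, and the multinomial check is there to show it.

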1.3 Hypothesis and Study Aims

The overarching hypothesis is that VTEL high-intensity functional circuit exercise in older HIV+ Veterans will improve the advanced aging phenotype and attenuate DNAm epigenetic processes underlying aging. We will explore the use of DNAm Age as an innovative biomarker that can predict adaptation to exercise by testing its association with exercise outcomes. Our experimental approach includes a 12-week VTEL exercise intervention in 80 older HIV+ Veterans who are randomized to exercise or standard of care sedentary control groups with the specific aims:

AIM 1. To determine the effect of VTEL exercise compared to control on:

- 1.1 Cardiorespiratory fitness, anaerobic threshold, and O₂pulse based on gas exchange at peak exercise
- 1.2 Sarcopenia defined by the European Working Group on Sarcopenia⁴⁴
- 1.3 Frailty defined by the Fried Phenotype⁴⁵ and the Veterans Aging Cohort Study (VACS) Index²⁷

AIM 2. To investigate the effect of VTEL exercise on DNAm Age²⁰ as a biomarker of advanced aging

AIM 3. To determine the effect of VTEL exercise on systemic inflammation by measure of:

- 3.1 DNA methylation of genes encoding pro-inflammatory cytokines in leukocytes (transcriptional regulation)
- 3.2 Corresponding systemic levels of pro-inflammatory cytokines IL-6 and IL-18 (protein expression)

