Blood samples will be collected and assayed per the specific aims during the study period at laboratories located at the Baltimore and Atlanta VAMCs and Emory University. In addition, blood samples will be stored for future testing (banked) at laboratories located at the Baltimore and Atlanta VAMCs. All blood specimens will be stored with study ID and code numbers as the only identifiers. Results of laboratory assays from the study will be labeled only with study ID and code numbers. Any specimen remaining after testing at the off-site laboratory will be destroyed per written a priori agreement with the laboratory director and PIs per VA regulations. Human research protection of all blood samples regardless of when blood samples assays are performed is under the prevue of the site performing the testing.

Data from Polar heart rate monitors cannot be analyzed in aggregate without extraction of the data from the individual monitors. To do so, data from each individual monitor of participants in the VTEL exercise group will be uploaded to the Polar company commercial server using a VA approved USB interface and access to a confirmed secure non-VA internet server at each enrollment site. Data on the HR monitor has no PHI and is limited to heart rate, year of birth, and study ID number. This information will be temporarily stored on the Polar server. The file with linkage of the study ID number to PHI will always remain behind the VA server at all times and is never released to Polar. Therefore, there is no PHI in the storage, extraction, and transfer of data from the Polar monitors. Heart rate data is essential for exercise research and there is no available VA system that can perform this function.

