Inflammatory Biomarkers: Testing of inflammatory biomarkers will occur at each respective enrollment site using the same kits since procedures are very standardized. We appreciate that change in plasma levels of cytokines can vary greatly between and within individuals. Our analysis plan takes this point into consideration by including change in cytokines as an independent variable in models of the primary and secondary outcomes. Changes in plasma levels will be calculated pre/post intervention and will be tested for association with changes in outcomes as well as between group differences.

DNA Methylation Assay: Samples will be tested for DNA methylation in the laboratory of [name] in Atlanta using established methods as previously described.^{23,58,78} Samples from Baltimore participants will be shipped directly to [name] lab. In sum, [name] will conduct a comprehensive interrogation of epigenome-wide CpG sites using the Illumina Infinium Methylation EPIC (850K) BeadChip. The 850K chip covers 99% of the NCBI Reference Sequence (RefSeq) genes, with sites covering the promoter, untranslated regions, and gene body, >95% of CpG islands, enhancer regions from FANTOM5 and ENCODE, as well as differentially methylated sites across tissue types. The EZ DNA Methylation Kit (Zymo Research, Orange CA) will be used to bisulfite-convert 0.5 µg of gDNA per sample. Bisulfite-converted DNA samples will be whole-genome amplified, enzymatically fragmented, and purified. Samples will be hybridized to the array. The array will then be fluorescently stained, scanned, and assessed for fluorescence intensities to quantify the methylation levels of each DNAm site.

Blood Banking: Blood sampling will include additional volume for future testing related to cardiometabolic disease and aging. These samples will be stored at the Atlanta and Baltimore VAMCs.

Clinical Data: Medical history and clinical laboratory values will be collected at the eligibility visit by a research clinician. Data will include comorbid conditions, medication use, CD4 cell count and HIV-1 PCR level, and other clinical labs included in the VACS Index. Both the participant and review of medical records will be used as source of the data.

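### Cytokine change is planned as a predictor in the outcome models and exercise fidelity in the ANOVA models; both arise after randomisation, and nothing keeps them out of the between-arm estimate

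*Combined protocol and SAP*

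**What the plan says.** The primary objective in section 1.1 is a comparison of VTEL exercise with sedentary controls.

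- **Outcome models (2.3.e, Aims 1 and 2).** "ANOVA models will be used with dependent variables of cardiorespiratory fitness" (VO2peak and the 2-minute step test) and DNA Age. Sarcopenia and frailty get logistic or multinomial models.
- **Between-arm test (2.3.e).** "ANCOVA will be used to test for between group difference by time (pre/post exercise"). Baseline performance, demographics and clinical features go into models that are not further identified. The Aim 3 paragraph repeats the pattern: ANOVA for the 12-week change in methylation, ANCOVA for the between-group difference.
- **Fidelity (2.3.e).** "Treatment fidelity will be measured as percent of AEX time at target heart and entered in ANOVA models". On the source of the data, 2.3.d says "data from each individual monitor of participants in the VTEL exercise group will be uploaded to the Polar company commercial server", and 3.2.a describes the chest-strap recording in the training sessions. For the other arm, 3.1 says "Participants in the Control Group will be instructed to maintain their baseline sedentary lifestyle".
- **Training time (2.3.e).** If 36 sessions do not fit into 12 weeks, total training time enters the analysis. How it enters is not stated.
- **Cytokines (3.3.b, Inflammatory Biomarkers).** Variability in cytokine change is handled by "including change in cytokines as an independent variable in models of the primary and secondary outcomes". The next sentence says that the changes "will be tested for association with changes in outcomes as well as between group differences". Section 1.3 lists as Aim 3.2 "Corresponding systemic levels of pro-inflammatory cytokines IL-6 and IL-18 (protein expression").

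No section calls one model the primary between-arm analysis, fixes its covariates, restricts fidelity to the exercise arm, or labels the models containing cytokine change as exploratory.

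**The concern.** Randomisation protects a comparison of arms adjusted for baseline variables. It does not protect one adjusted for something the intervention may have changed.

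The cytokine sentence is the firmer part, because it is a stated rule: cytokine change goes into models of the primary and secondary outcomes. If arm is in the same model, its coefficient answers a different question from the one in section 1.1.

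The fidelity sentence is an ambiguity. It uses the same term, ANOVA models, that 2.3.e uses for VO2peak, the step test and DNA Age, and it names no arm. Controls have no aerobic sessions during the 12 randomised weeks, so they have no fidelity value. It does not touch the logistic and multinomial models for sarcopenia and frailty; the cytokine sentence covers all primary and secondary outcomes.

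At stake is which coefficient is reported as the trial's between-arm result, and whether it has a causal reading.

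**Working it through.** **1. The plan's own figures.** The sample-size table in 2.3.e rests on paired t-tests. For DNAm Age at pre/post correlation 0.3, the SD of the change is √(10.8² + 10² − 2×0.3×10.8×10) = √151.84 = 12.3. With a change of 68.7 − 62 = 6.7, two-sided alpha 0.05 and 80% power this gives 29; correlations 0.5 and 0.7 give 21 and 14. All three match. They are within-person figures, so the plan states no between-arm power to compare with what follows.

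**2. Cytokine change in a two-arm model.** Work in SD units. Let exercise shift cytokine change by a, let the within-arm correlation of cytokine change with outcome be ρ, and let the randomised effect be d. Adjusting for cytokine change gives

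arm coefficient = d − a×ρ.

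Assumed values, none from the documents:

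| a | ρ | a×ρ (SD) |
|---|---|---|
| 0.2 | 0.1 | 0.02 |
| 0.5 | 0.3 | 0.15 |
| 0.8 | 0.5 | 0.40 |

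Simulation with d = 0.6 and 40 per arm gave 0.59, 0.46 and 0.20, against 0.58, 0.45 and 0.20 from the formula. If ρ reflects mediation alone, a×ρ is the part of the effect that has been removed. If ρ reflects unmeasured shared causes, a×ρ is bias. When a×ρ has the opposite sign to d, the coefficient moves away from zero.

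**3. Fidelity in a two-arm model.** There are two ways to handle controls.

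- *Missing in controls, complete cases.* Only exercisers remain, arm is constant, and its effect cannot be estimated. The multiple imputation in 2.3.e is for dropouts; it cannot supply a quantity that is undefined in controls.
- *Coded 0 in controls.* With 1:1 allocation, exercise-arm mean μ and SD s, the squared correlation of arm with fidelity is R² = (μ/2)² / [(μ/2)² + s²/2], and the standard error of the arm term is multiplied by √[1/(1 − R²)].

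| Assumed μ, s | R² | 1/(1 − R²) | SE multiplier |
|---|---|---|---|
| 0.50, 0.20 | 0.0625/0.0825 = 0.758 | 4.1 | 2.03 |
| 0.70, 0.15 | 0.1225/0.13375 = 0.916 | 11.9 | 3.45 |
| 0.70, 0.10 | 0.1225/0.1275 = 0.961 | 25.5 | 5.05 |

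**4. Bias as well as imprecision.** Illustration using the size of the DNAm Age change (6.7), SD 10.4, correlation 0.5, 40 per arm, fidelity 0.6 (SD 0.2), controls 0, 4,000 simulated trials per setting. Without fidelity, power is about 0.90. With fidelity:

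| Share of effect that scales with fidelity | Arm estimate | Power |
|---|---|---|
| 0% | 6.7 | 0.27 |
| 50% | 3.3 | 0.11 |
| 100% | 0.1 | 0.05 |

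Now set the true effect to zero and let fidelity correlate c with the outcome residual through an unmeasured cause. The arm term is expected at −c×10.4×√0.75×(0.6/0.2), about −27c: −5.4, −8.1 and −13.5 for c = 0.2, 0.3 and 0.5. Simulated means were −5.4, −8.3 and −13.8 (fidelity was truncated to 0–1, which reduces its SD). Rejection was 0.20, 0.39 and 0.84, against about 0.05 without fidelity. A negative c reverses the sign.

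The 6.7 years is a rise taken from an observational antiretroviral study, so it serves only as a scale.

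**The case against.** The strongest reply is that the plan already separates the two jobs. Section 2.3.e gives the between-group difference to ANCOVA and places fidelity only in ANOVA models; the Aim 3 paragraph repeats that division. It also describes each participant as their own control and sizes the trial with paired tests, which fits ANOVA meaning pre/post change. Fidelity is defined only where there is aerobic exercise time, so an exercise-arm analysis is its natural home. On cytokines, the sentence that follows speaks of association with outcome change and of between-group differences, which suggests correlational work.

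Most of this stands for fidelity: the two-arm reading is permitted but is not the likeliest. It does not settle the matter, because no sentence limits fidelity to one arm or closes the ANCOVA's covariate list. For cytokines the reply is weaker. The association sentence adds tests; it does not withdraw cytokine change from the primary and secondary outcome models, and nothing says that arm is absent from them.

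A reader might infer that the plan adjusts its main between-arm result for fidelity. The documents do not support that: no sentence puts fidelity in the ANCOVA. Nor do they say that a cytokine-adjusted arm coefficient is the trial result.

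**Conclusion.** The point holds as a specification gap, led by the cytokine sentence. Where cytokine change sits in a model that also estimates the arm effect, the arm coefficient is not the randomised effect. For fidelity and total training time the gap is one of wording. If the between-arm result comes from the ANCOVA with baseline covariates, as 2.3.e can fairly be read, no harm arises from either.

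No reliable size can be given. The documents state no fidelity distribution, no coding for controls, no cytokine shift and no mediated share, so the figures above show mechanism and possible scale only. Two tempting inferences should be resisted. One is that the trial will lose a particular amount of power; that depends wholly on assumed inputs. The other is that the estimate can only shrink towards zero; shared causes can push it either way and can produce false positives.

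It is worth fixing before analysis, because the correction is cheap and removes a choice that could otherwise be made after seeing data.

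**What to change.** - **Section 2.3.e.** State that the between-arm result comes from the ANCOVA already planned, and from the logistic or multinomial models for sarcopenia and frailty, with randomised arm, baseline value and pre-specified baseline covariates only, and no post-randomisation covariates.
- **Section 2.3.e.** Use fidelity, and total training time if it is used, only in a dose-response analysis within the exercise arm.
- **Section 3.3.b.** Limit cytokine change as an independent variable to association or mediation models labelled exploratory. Keep its between-group difference as the Aim 3.2 result.

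The cost is a few sentences in two sections. No new data are collected and no planned analysis is lost.
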